Clinical guidelines recommend that treatment consists of a combination of medical, surgical and non-pharmacological interventions such as patient education, physical- and occupational therapy, cognitive-behavioral therapy, nutritional counseling and self-management strategies¹³⁻¹⁶. The most frequent treatment of BPD is pharmacological¹⁷. Despite not being generally recommended for treatment of back pain disorders¹⁸, opioids are prescribed in up to 66% of patients¹⁹. The prevalence of concomitant substance abuse disorder in BPD patients receiving opioid treatment is up to 43%¹⁹. Previous studies fail to establish, which type of back pain patients are prescribed opioids and which specific other psychiatric comorbidities than substance abuse are linked to higher opioid consumption. It does seem, that patients with a high burden of psychiatric comorbidity, have a higher rate of opioid misuse, although studies are old, small and heterogeneous²⁰⁻²³. Several studies on the association between back pain and psychiatric disorders, focusing on depression and anxiety disorders, have been conducted. However, these studies have several limitations: they do not include other types of psychiatric comorbidity²⁴⁻²⁹ and they are often based on questionnaires. Including nationwide data sources might minimize potential selection bias. Furthermore, many studies have focused on large heterogeneous groups of patients with nonspecific back pain symptoms instead of being based on BPD diagnosis as defined by the ICD-10³⁰. The majority of studies do not compare different BPD-diagnosis when assessing psychiatric comorbidity.^{24 27 31-33}

To more accurately assess the risk of psychiatric comorbidity in patients with back pain disorders, population-based registry data could be utilized. The Danish health registries are generally considered to have a high validity, however there are limitations to consider, as described in previous studies on each registry^{34 35 36 37}, which has to be taken into consideration when interpreting results based on data from these registries.

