Psychiatric comorbidity will be defined as the presence of any of the following diagnosis, according to ICD-10 classification³⁰, obtained from the National Patient Registry – Psychiatry (NPD-Psych), covering all inpatient and outpatient psychiatric services in Denmark in the time period 1th January 2007 to 31th December 2017: Organic, including symptomatic, mental disorders (F00-DF09), Mental and behavioral disorders due to psychoactive substance use (F10-F19), Schizophrenia, schizotypal and delusional disorders (F20-F29), Mood [affective] disorders (F30-F39), Neurotic, stress-related and somatoform disorders (F40-F48), Behavioral syndromes associated with physiological disturbances and physical factors (F50-F59), Disorders of adult personality and behavior (F60-F69), Mental retardation (F70-F79), Disorders of psychological development (F80-F89), Behavioral and emotional disorders with onset usually occurring in childhood and adolescence (F90-F98) and, Unspecified mental disorder (F99). To qualify as a psychiatric comorbidity to back pain disorder, we define that the psychiatric diagnosis must be given no earlier than three years prior to back pain disorder diagnosis and no later than three years after.

Study 1) Prevalence of psychiatric comorbidity in back pain disorders

Psychiatric comorbidity in Back Pain Disorders
Risk, treatment and pharmaco-epidemiological analysis

Aim: 1) To estimate prevalence of psychiatric comorbidity in patients with BPD compared to patients without BPD and 2) To estimate prevalence of psychiatric comorbidity in patients with unspecific back pain (UBP) compared to the background population and to patients with a specific back pain (SBP) in a Danish nationwide cohort from 2010-2014.

Hypothesis: 1) There is a higher risk of psychiatric comorbidity in BPD patients compared to the background population and 2) UBP patients have a higher risk of psychiatric comorbidity compared to patients with specific BPD.

Design: The study will be a nationwide register-based matched cohort study.

Procedure: Selected BPD patients with the following diagnosis will be identified via the DNPR: Spondylopathies DM45-49, Other dorsopathies DM 50-54 and Segmental and somatic dysfunction DM99. Each patient will be matched 1:5 on age and sex with patients without back disorders by random at Statistics Denmark³⁸. The selection of diagnosis is to be able to match the population with non-BPD patients in the Danish registries.

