Procedure: BPD patients will be identified via the DNPR. Pharmacological treatment of BPD will be defined as any treatment with the following drugs: NSAID (ATC: N01A*), Acitomenophen (ATC: N02BE01), Opioids (N02A*)¹³. Pharmacological treatment for psychiatric comorbidity will be defined as any treatment with the following drugs: Antipsychotics (ATC:N05A), Antidepressants (ATC: N06A), Selective Serotonin Reuptake Inhibitors (SSRI) (ATC: N06AB), and anxiolytics (ATC: N5B*)⁴¹. Pharmacological treatment that can be used in the treatment of both BPD and psychiatric disorders will be defined as any treatment with the following drugs: Antiepileptics (ATC: N03A) and Tricyclic antidepressants (ATC: N06AA). All data on pharmacological treatment will be identified using the Register of Medicinal Products Statistics⁷. From time of BPD diagnosis and the following three years, pharmacological treatment for both somatic illness and psychiatric comorbidity in Daily Defined Dosage (DDD) per year will be calculated⁴².

Information on somatic comorbidity for calculation of Charlson Comorbidity index³⁹ (CCI) at time of BPD diagnosis, will be retrieved from the DNPR. Data on psychiatric comorbidity will be identified using NPD-Psych. Information on marital status, vital status, and immigration status will be retrieved from the Civil Registration System (CPR)³⁵. Patients that are not alive or have emigrated within three years after BPD diagnosis are considered lost to follow-up and excluded from the cohort. Descriptive data on the socioeconomic status, education level and equivalent available income will be retrieved from Statistics Denmark³⁸. All data comprising each variable will be retrieved from 1th of January 2007 to 31th of December 2017 (three years before and after study period).

Measures of outcome: Primary outcome is pharmacological treatment in DDDs defined as high (above the 50th percentile and low (below the 50th percentile) of pain medication. Secondary outcome is psychiatric medication in BPD patients with psychiatric comorbidity in DDD's defined according to high (above the 50th percentile) and low (below the 50th percentile) dosages of pain medication.

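### Study 3 counts psychiatric medication with a drug list that has no class specific to dependence, dementia, attention-deficit or sleep disorders, although its cohort admits every F00-F99 diagnosis

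*Combined protocol and SAP*

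**What the plan says.** **Cohort.** Under Setting and study population, psychiatric comorbidity is a diagnosis in any of eleven ICD-10 blocks that together span F00-F99. Four of them matter here: "Organic, including symptomatic, mental disorders (F00-DF09"), "Mental and behavioral disorders due to psychoactive substance use (F10-F19"), "Behavioral syndromes associated with physiological disturbances and physical factors (F50-F59") and "Behavioral and emotional disorders with onset usually occurring in childhood and adolescence (F90-F98"). The Introduction treats every psychiatric diagnosis as relevant and presents the project as going beyond anxiety and depression. The secondary analysis of Study 3 takes patients from this cohort who also received drug treatment for back pain, with no narrowing of the diagnoses.

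**Drug lists.** Study 3, Procedure, gives a closed list: "Pharmacological treatment for psychiatric comorbidity will be defined as any treatment with the following drugs: Antipsychotics (ATC:N05A), Antidepressants (ATC: N06A"), followed by "Selective Serotonin Reuptake Inhibitors (SSRI) (ATC: N06AB), and anxiolytics (ATC: N5B"*). A separate dual-use group, usable for back pain or psychiatric illness, consists of "Antiepileptics (ATC: N03A) and Tricyclic antidepressants (ATC: N06AA"). The plan does not say whether the dual-use group counts toward the secondary outcome.

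**Use.** The secondary outcome is psychiatric medication in DDDs, compared between patients above and below the median pain-medication dose (hypothesis 2). In addition, the main pain-dose analysis adjusts for whether psychotropic drugs were used. The Statistics paragraph does not define that covariate.

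**The concern.** The plan is broad when it decides who enters the cohort and narrow when it measures their treatment. A patient who enters with a substance-use diagnosis and receives only a drug specific to dependence contributes zero psychiatric DDDs. The same holds for a patient with dementia, an attention-deficit disorder or a non-organic sleep disorder who is treated only with drugs specific to that condition.

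The first consequence is that the reported amount of psychiatric medication is too low. The second concerns hypothesis 2. If the uncounted share is not the same in the high and low pain-dose groups, the contrast is distorted, and a null, positive or reversed result could not be told apart from incomplete capture. The third is conditional: if the psychotropic-use covariate is built from the same list, some treated patients are coded as untreated in the main analysis.

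**Working it through.** The documents give no sample size, power, event count or drug-use figure on this point, so there is no stated figure to reproduce. The check has two parts.

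**1. Coverage.** Inputs: the diagnosis blocks (Setting and study population) and the listed ATC stems (Study 3, Procedure), which are N05A, N06A, N06AB, N5B (read here as N05B), N03A and N06AA. Two assumptions come from the standard classifications, because the plan does not spell them out. They are the conditions that sit in each ICD-10 block, and the ATC stem for each missing class.

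| Condition | Enters through | Specific class (assumed stem) | Under a listed stem? |
|---|---|---|---|
| Substance dependence | F10-F19, named in the plan | Dependence drugs (N07B) | No |
| Dementia | F00-F09, by block | Dementia drugs (N06D) | No |
| Attention-deficit disorders | F90-F98, by block | Psychostimulants (N06B) | No |
| Non-organic sleep disorders | F50-F59, by block | Hypnotics (N05C) | No |

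All four conditions are inside the cohort, and 0 of 4 classes are inside either list. Counting the dual-use group (N03A, N06AA) toward the outcome does not change this.

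**2. What omission does to the comparison.** Let R be the true ratio of psychiatric DDDs, high over low pain dose. Let uH and uL be the shares of those DDDs that fall in unlisted classes in the high and low groups. Each group's recorded total is its true total times (1 − u), so

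recorded ratio = R × (1 − uH) / (1 − uL).

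R, uH and uL are all assumed. With R = 1.2:

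| uH | uL | Calculation | Recorded ratio |
|---|---|---|---|
| 10% | 10% | 1.2 × 0.90/0.90 | 1.20 |
| 10% | 5% | 1.2 × 0.90/0.95 | 1.14 |
| 20% | 10% | 1.2 × 0.80/0.90 | 1.07 |
| 30% | 10% | 1.2 × 0.70/0.90 | 0.93 |
| 10% | 20% | 1.2 × 0.90/0.80 | 1.35 |

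Equal omission leaves the ratio unchanged and lowers only the level. Unequal omission moves the ratio either way. With R = 1.2 and uL = 10%, the recorded ratio falls below 1 only when uH exceeds 1 − 0.90/1.2 = 25%.

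The plan's analysis is a time-dependent Cox regression, not a ratio of DDD totals. The table therefore shows the mechanism and does not predict the planned estimate.

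**The case against.** **Core psychotropics are a legitimate construct.** Antipsychotics, antidepressants and anxiolytics are a recognisable group, and the plan cites a psychiatric prescribing guideline for its list. This would stand if the plan said that it meant to measure only those classes. It does not say so. It labels the list as treatment for psychiatric comorbidity and defines that comorbidity as F00-F99.

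**Many affected patients are still recorded.** Anyone in the four groups who also takes a listed drug is counted for that drug. This stands. The zero-DDD problem is confined to patients treated wholly with unlisted classes, and the documents do not show how many there are. A yes/no covariate is wrong only for patients with no counted drug at all.

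**The bias against hypothesis 2 is not shown.** A reader might infer that the omission must pull hypothesis 2 toward the null or reverse it, because the Introduction reports that "The prevalence of concomitant substance abuse disorder in BPD patients receiving opioid treatment is up to 43" per cent. The documents do not support that step. The figure is an upper limit from cited literature, and it is a prevalence of diagnoses, not a share of DDDs. The cohort instead uses hospital psychiatric diagnoses, which the Introduction says capture only severe illness. Pain medication also pools NSAIDs, acetaminophen and opioids, so an above-median pain dose need not mean heavy opioid use. Nothing in the plan places patients with dementia, attention-deficit or sleep disorders in the high-dose half.

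**Conclusion.** The mismatch between cohort and outcome is in the text, and nothing elsewhere in the plan repairs it. If the plan is followed as written, the secondary outcome of Study 3 understates psychiatric medication use. The high versus low pain-dose comparison is biased only if the uncounted share differs between the groups, and neither the direction nor the size can be derived from the documents. The effect on the covariate depends on whether it uses the same list, which the plan leaves open.

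This is a modest point on a secondary outcome, worth correcting because the correction is cheap. It rests on the usual ICD-10 block contents for dementia, attention-deficit and non-organic sleep disorders, since only substance use is named directly. It does not rest on any claim that the listed drugs are never used in these disorders. The claim is only that no class specific to them is listed.

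**What to change.** - Extend the psychiatric drug list in Study 3, Procedure, with the classes specific to dependence, dementia, attention-deficit and sleep disorders, taken from the same register. Confirm the codes against the ATC edition that the plan cites.
- Keep dependence drugs separate from the pain opioids, so that no dispensing counts in both totals.
- Use the extended list for the secondary outcome and for the psychotropic-use covariate, and define that covariate explicitly. State whether the dual-use group counts toward the outcome.
- Report psychiatric DDDs by class as well as in total.
- Keep two sensitivity analyses: one with the plan's present list, and one restricted to patients with F20-F48 diagnoses.

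The F20-F48 restriction should not become the main analysis. It would cut against the stated interest in all psychiatric diagnoses and drop patients who have only a substance-use diagnosis. Patients with both F20-F48 and F10-F19 diagnoses would still have uncounted dependence drugs under the present list.

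The cost is a few more codes and a more heterogeneous DDD total, which the reporting by class makes visible. If the sponsor prefers the narrow list, the minimum is to state the reason, name the outcome accordingly and add the extended list as a sensitivity analysis.

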Measures of outcome: The outcome is type of treatment for BPD (surgical, pharmacological and other types of treatment)

Statistics: We will use Fisher's exact test and t-test to compare patients' baseline characteristics with 95% confidence intervals (CI) and p-values. For each treatment type we will use logistic regression model to investigate differences in outcome distribution between patients with and without psychiatric comorbidity. The logistic regressions will be performed with 95% CI adjusted for the following confounders: age, sex, CCI, level of education, equivalent available income, type of BPD (IBD, DBD or UBP) and marital status.

Study 3) Effect of psychiatric comorbidity in pharmacological treatment of BPD.

Aim: 1) To compare dosages of pharmacological treatment in BPD patients with and without the presence of psychiatric comorbidity in a nationwide Danish cohort study in 2010-2014. 2) To compare high vs. low dosages of pharmacological treatment for BPD in patients with BPD and psychiatric comorbidity.

Hypothesis: 1) Patients with BPD and psychiatric comorbidity are prescribed a higher dosage of pain medication for BPD compared with BPD patients without psychiatric comorbidity. 2) BPD patients with a psychiatric comorbidity with a high (defined as above the 50th percentile) vs. low (defined as below the 50th percentile) dosage of pain medication are also prescribed higher dosages of psychiatric medication.

Design and study population: The study will be a nationwide register-based cohort study. The study population consists of patients with BPD that received pharmacological treatment for BPD. In the secondary analysis the study population consists of patients with BPD and a psychiatric comorbidity, who received pharmacological treatment for BPD.

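### Study 3 states its hypotheses as dosage but measures DDDs per year, an amount dispensed that rises with length of treatment as well as with daily dose

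*Combined protocol and SAP*

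**What the plan says.** Under Study 3, Hypothesis, patients with back pain disorder and psychiatric comorbidity "are prescribed a higher dosage of pain medication for BPD compared with BPD patients without psychiatric comorbidity". The second hypothesis is that comorbid patients above the median for pain medication "are also prescribed higher dosages of psychiatric medication".

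Under Study 3, Procedure, the measurement window is "From time of BPD diagnosis and the following three years", and within it "pharmacological treatment for both somatic illness and psychiatric comorbidity in Daily Defined Dosage (DDD) per year will be calculated". The same section fixes the window for everyone: "Patients that are not alive or have emigrated within three years after BPD diagnosis are considered lost to follow-up and excluded from the cohort".

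The outcomes section of Study 3 then states: "Primary outcome is pharmacological treatment in DDDs defined as high (above the 50th percentile and low (below the 50th percentile) of pain medication". The secondary outcome is also an amount: "Secondary outcome is psychiatric medication in BPD patients with psychiatric comorbidity in DDD's", compared between the high and low pain-medication groups.

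Eligibility sets no minimum length of treatment: "The study population consists of patients with BPD that received pharmacological treatment for BPD".

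Under Study 3, Statistics, time-dependent Cox models are to examine dosage over time. The adjustment sets hold demographic and socioeconomic variables and the Charlson index; the first model adds presence of psychopharmacological treatment. Neither set contains days treated, number of prescriptions or any other measure of duration. No section defines dose per treated day, treatment episodes or days covered.

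**The concern.** A DDD count over a fixed calendar period measures consumption. It does not show whether a high value comes from a high daily dose or from many days of use. Because patients who die or emigrate within three years are excluded, the denominator is the same calendar time for everyone and takes no account of time on drug. Any user of a listed drug is eligible, so time on drug may vary widely.

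If psychiatric comorbidity goes with longer analgesic use at an unchanged daily dose, the comorbid group will have more DDDs per year and more members above the median. In the words of the hypothesis, that would be written up as a higher dosage. Longer treatment and higher dosing are different findings, and a reader of the results could not tell which had occurred.

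In the second analysis, duration can enter both the grouping variable and the outcome. If some patients tend to stay on prescribed medicines of both kinds for longer, the two DDD totals will be associated even with no relation between the daily doses.

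**Working it through.** The plan gives no expected DDD value, effect size or sample size for Study 3, so there is no figure of its own to reproduce. The check is on the measure itself. From the documents come the unit (DDD per year), the three-year window, the fixed follow-up and the median split. All doses and durations below are assumptions chosen to show the arithmetic.

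**1. Formula.** As a three-year average, DDD/year = (daily dose in DDD × days treated) / 3. As a yearly total, DDD in year k = daily dose × days treated in year k. Both are products of dose and time.

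**2. Same dose, different duration (1 DDD/day, continuous from diagnosis).**
- 18 months: 1.5 × 365 = about 548 DDD. Three-year average 548/3 = about 183. Yearly totals 365, about 183, 0.
- 9 months: 0.75 × 365 = about 274 DDD. Three-year average 274/3 = about 91. Yearly totals about 274, 0, 0.
- Ratio: 183/91 = about 2.0 on the average; 365/274 = about 1.33 in year 1, with the rest appearing as use in year 2. The daily dose is identical throughout.

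**3. Different dose, same value.** 2 DDD/day × 90 days = 180 DDD and 1 DDD/day × 180 days = 180 DDD. Both average 180/3 = 60 DDD/year. If both courses start at diagnosis, both also have yearly totals of 180, 0, 0, so yearly totals do not separate them either.

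**4. When a lower dose gives a higher value.** With dose ratio r and duration ratio t (comorbid over non-comorbid), the DDD/year ratio is r × t, which exceeds 1 only if t > 1/r. For r = 0.8 the threshold is 1/0.8 = 1.25.

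**5. Effect on a median split (simulation, all distributions assumed).** Daily dose is log-normal (median 1 DDD/day, log-SD 0.6). Days treated are log-normal (median 120, log-SD 1.0, capped at 1,095). The comorbid share is 5% or 20%, n = 400,000, and the split is at the pooled median of the three-year average. The figures are odds ratios for being classed high, comorbid versus not; ranges cover the two shares. They do not predict the planned Cox result.

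| Dose ratio | Duration ratio | Split on DDD/year | Split on dose per treated day |
|---|---|---|---|
| 1.0 | 1.5 | 1.71–1.74 | about 1.0 |
| 1.0 | 2.0 | 2.61–2.66 | about 1.0 |
| 0.8 | 1.1 | about 0.83 | about 0.55 |
| 0.8 | 1.25 | 0.98–1.00 | about 0.56 |
| 0.8 | 1.5 | about 1.29 | about 0.55 |

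The direction reverses only beyond the threshold in step 4. Below it, the DDD/year split still shows the lower dose as lower, though less clearly than the per-treated-day split does.

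**The case against.** DDD/year is a valid and openly stated measure of consumption. The thesis-level aim names utilisation as well as dosage, and the Introduction describes the gap in terms of opioid consumption, so total amount may be what the investigators want. This stands, and it is why the first remedy is to reword. It does not rescue the present text, because Study 3's own aims, hypotheses and analysis descriptions say dosage.

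The unit may mean three yearly values entered in the time-dependent model. That reading is as natural as a single average, and it would show when use occurred. It is therefore too strong to infer that the plan could never tell a short course from a long one. Mixing within each year remains, however, and the high/low split is not defined as yearly or cumulative.

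A reader might also infer that longer treatment at a lower dose would always be reported as a higher dosage. The arithmetic does not support that: it happens only beyond the threshold shown. Nor do the documents show that Study 3 will reach a wrong conclusion. They contain no data on treatment length by comorbidity, and the event in the Cox models is not defined, so the model's output cannot be predicted.

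Finally, DDDs per quarter with a dispensing could not simply take over the word dosage. At 1 DDD/day, 15 treated days in a quarter give 15 and 90 days give 90, a six-fold difference at the same dose. One pack covering two quarters would halve the measured duration and double the intensity. This objection stands and limits what the supporting analysis can carry.

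**Conclusion.** The concern holds as a mismatch between construct and measure. Study 3 asks about dosage and measures annual amount dispensed, and no derived variable or adjustment term separates dose while treated from time treated. A higher dosage can therefore be reported where only treatment length differs. At equal daily dose, the apparent ratio equals the duration ratio under a three-year average (two-fold in the illustration) and is smaller in the first year under yearly totals (1.33-fold). For a lower dose the statement is conditional on the duration ratio exceeding the inverse of the dose ratio. The same mixing applies to both variables in hypothesis 2.

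The size in practice is unknown, because it depends on how treatment length differs by comorbidity, which the documents do not give. The point is minor: the planned analysis remains usable as a study of amount, and what needs correcting is the wording of its claim.

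**What to change.** 1. Restate the Study 3 hypotheses, outcomes and conclusions as annual amount dispensed (DDD/year), and say whether the high/low split uses yearly or three-year totals.
2. Add two supporting analyses from the prescription data: duration (for example, number of quarters with at least one dispensing) and approximate intensity (DDDs per quarter with a dispensing, or per estimated treated day).
3. Claim a dose difference only if the intensity analysis supports it; otherwise report a difference in amount, with duration alongside.

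The cost is two derived variables and repeat model runs. No new data should be needed, on the inference that yearly totals counted from each patient's diagnosis date already require dated prescription records; the plan does not state this. Intensity stays approximate, because duration within a quarter, pack size and the pooling of drug classes still affect it, and the report should say so.

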Statistics: We will use Fisher's exact test and t-test to compare patients' baseline characteristics with 95% confidence intervals (CI) and p-values. Time dependent Cox regression will be performed separately for patients with specific and unspecific BPD to examine dosage of pharmacological treatment over time comparing patients with and without psychiatric comorbidity. The analysis will be performed with 95% CI and adjusted for the following confounders: age, sex, CCI, level of education, equivalent available income, marital status and the presence of psychopharmacological treatment.

To examine dosage of psychopharmacological treatment over time comparing patients with psychiatric comorbidity and low vs high dose of pharmacological treatment of BPD, time dependent Cox regression will be performed reporting 95% CI and adjusting for the following confounders: age, sex, CCI, level of education, equivalent available income, marital status.

Psychiatric comorbidity in Back Pain Disorders
Risk, treatment and pharmaco-epidemiological analysis

Ethics

All studies will be based on national clinical registries and approval is obtained by The Danish Health Data Board and the Danish Data Protection Agency (18/3337). According to Danish law, further ethical approval is not required for purely registry-based studies. All data will be stored on Statistics Denmark's servers and will be anonymized ensuring no patients can be identified.

PhD Outline

The PhD will be conducted within a timeframe of three years (six semesters).

	1st semester	2nd semester	3rd semester	4th semester	5th semester	6th semester
Data collection	X					
PhD Courses	X	X	X			
Data analysis		X	X	X	X	
Writing articles			X	X	X	X

References

1. Hawker GA. The assessment of musculoskeletal pain. *Clinical and experimental rheumatology* 2017;35 Suppl 107(5):8-12.

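### Study 3 names time dependent Cox regression for two dosage questions but defines no event: the secondary analysis cannot be run as written, and a primary hazard ratio would mix dose with timing

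*Combined protocol and SAP*

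**What the plan says.** Study 3, Statistics, gives the method for the first comparison (patients with and without psychiatric comorbidity): "Time dependent Cox regression will be performed separately for patients with specific and unspecific BPD to examine dosage of pharmacological treatment over time". For the second comparison, within patients with comorbidity, the groups and method are "low vs high dose of pharmacological treatment of BPD, time dependent Cox regression will be performed reporting 95% CI".

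The two hypotheses concern levels of use. Under the first, patients with comorbidity "are prescribed a higher dosage of pain medication for BPD compared with BPD patients without psychiatric comorbidity". Under the second, those with a high rather than low "dosage of pain medication are also prescribed higher dosages of psychiatric medication".

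Measures of outcome follows the same line. For pain medication: "Primary outcome is pharmacological treatment in DDDs defined as high (above the 50th percentile and low (below the 50th percentile) of pain medication". For psychiatric medication: "Secondary outcome is psychiatric medication in BPD patients with psychiatric comorbidity in DDD's defined according to high" or low pain-medication dose.

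Study 3, Procedure, fixes the observation window: "From time of BPD diagnosis and the following three years, pharmacological treatment for both somatic illness and psychiatric comorbidity" is to be calculated in DDD per year. It also states: "Patients that are not alive or have emigrated within three years after BPD diagnosis are considered lost to follow-up and excluded from the cohort".

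**The concern.** A Cox model relates covariates to the rate at which a defined event occurs. Calling it time dependent means that at least one covariate, or its effect, changes during follow-up. Study 3 supplies neither an event nor such a variable. What it wants to compare is an amount, or a yes/no status derived from an amount.

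Two analysts could therefore follow this text and produce different results. If the event is chosen once the data are in hand, the main result of Study 3 is open to selection. A hazard ratio might also be reported as evidence of a higher dosage when part of it reflects only how early the drug was dispensed.

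**Working it through.** The plan states no sample size, event count or effect size for Study 3, so there is no figure to reproduce. The main check sets the sections side by side.

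**What a Cox analysis needs, and what Study 3 gives**

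| Element | Primary (pain medication) | Secondary (psychiatric medication) |
|---|---|---|
| Origin and window | Can be inferred: BPD diagnosis, three years | Same |
| Event | Not stated; crossing the 50th percentile is the only candidate | None can be derived |
| Event date | Not stated | Not stated |
| Time-dependent variable | Not stated | Not stated |
| Stated outcome | High/low status in DDD | Psychiatric DDD by pain-dose group |

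In the secondary analysis the 50th percentile is set on pain medication and defines the groups. No cut-off for psychiatric DDD appears anywhere, so there is nothing to cross.

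**Censoring.** BPD diagnoses run to 31 December 2014 and data to 31 December 2017. Patients who die or emigrate within three years are removed. Every analysed patient therefore has the full three years, and high/low status is observed for all. Early loss to follow-up gives no reason for a survival model.

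**What a percentile-crossing hazard ratio would measure.** This part is illustrative. All inputs are assumed, and the models are unadjusted with comorbidity fixed at baseline.

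*Simulation 1.* Annual DDD over three years is log-normal, with between-person SD 1.2 and within-person SD 0.6. 10% of patients have comorbidity and 24% of years have zero use. A grouped proportional hazards model is fitted to years 1 to 3. The event is either the first year above the annual median, or cumulative DDD passing the three-year median.
- True dose ratio 1.00: hazard ratios 1.00 and 1.00.
- True dose ratio 1.25: hazard ratios 1.16 and 1.20. Over 27 input sets the ranges are 1.11 to 1.25 and 1.15 to 1.30.
- Equal mean three-year dose, comorbid group using earlier (year weights 1.4/1.0/0.6): hazard ratios 1.08 and 1.05, high/low odds ratio 0.99.
- Equal mean three-year dose, comorbid group using later (0.6/1.0/1.4): hazard ratios 0.89 and 0.93, odds ratio 0.99.

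*Simulation 2.* 20,000 patients, 20% with comorbidity, three-year DDD with log-SD 0.8, spread over 36 months. The event is cumulative DDD reaching the three-year median.

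| Assumed scenario | High: without vs with comorbidity | Odds ratio | Hazard ratio |
|---|---|---|---|
| Same dose, comorbid group earlier | 50.1% vs 49.4% | 0.97 | 1.12 |
| 30% higher dose, same timing | 47.8% vs 58.5% | 1.54 | 1.39 |
| 30% higher dose, comorbid group later | 47.6% vs 59.6% | 1.62 | 1.23 |

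The odds ratios follow from the percentages, for example (0.585/0.415)/(0.478/0.522) = 1.54. Between the last two rows the dose effect set in the simulation is the same. The odds ratio barely changes, but the hazard ratio falls from 1.39 to 1.23 because of timing.

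**The case against.** An event left open makes the estimand unspecified, not shown to be wrong. If the event is cumulative DDD passing the three-year median, event status at three years is exactly the stated high/low outcome. In Simulation 1 the hazard ratio then agrees in direction with the dose ratio and is 1.00 at the null. The plan also speaks of dosage over time, so some sensitivity to timing may be intended. This stands for the primary analysis. A reader might infer that a Cox model there must give a wrong answer or cannot address the outcome at all; the documents do not support that.

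There is also a good reason why a time-dependent model might have been chosen. Materials and methods counts psychiatric diagnoses made up to three years after BPD diagnosis, so exposure can begin during follow-up. A three-year logistic analysis that ignored this would credit doses taken before the psychiatric diagnosis to the comorbid group. Study 2's split into prior and after groups does not cure it, because the after group is defined by later information. This also stands, and the fix must deal with it. But Study 3 never says that comorbidity is the time-dependent term.

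Two further inferences should be resisted. The plan does not say whether the percentile is annual or for the three-year total. That needs stating, but it affects logistic regression equally and is no argument against Cox. The first model also adjusts for psychopharmacological treatment without saying when it is measured. That is a separate, conditional issue and adds nothing to this point.

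Finally, the simulations contain no time-dependent term and no adjustment. They show only the principle that timing alone can move the hazard ratio.

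**Conclusion.** The point holds and should be settled before analysis. Both Study 3 dosage analyses name a model whose event, event date and time-dependent variable are undefined, while the hypotheses and outcomes are amounts. For the secondary analysis this is more than missing detail, since no event can be derived. For the primary analysis a percentile-crossing hazard ratio would usually share the direction of a dose difference, but it cannot by itself be read as a higher dosage.

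This rests on comparing the plan's own sections and needs no simulation. The simulated sizes depend wholly on assumed inputs, and the effect in the real data is unknown. The documents do not use the term hazard ratio; it is the usual output of the model they name.

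**What to change.** 1. **Primary.** Analyse high/low pain-medication status by adjusted logistic regression, separately for specific and unspecific BPD. State the period (annual or three-year total) and the population used to set the 50th percentile. Give the high-dose percentages with the odds ratio. Beside it, report a dose ratio from a model of annual DDD that allows zeros, for example a log-link GEE with robust standard errors.
2. **Hypothesis 2.** Model annual psychiatric DDD by high/low pain-dose group and report it as a concurrent association, since both are measured over the same three years.
3. **Exposure timing.** In the three-year logistic analysis, classify psychiatric comorbidity by diagnoses made up to the BPD diagnosis. In the annual DDD model, enter later diagnoses as time-varying, so that doses taken before a psychiatric diagnosis are not counted as exposed.
4. **If Cox is kept for the primary question,** define its event, event date and time-varying term, and word its conclusion as time to crossing the threshold.

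The cost is SAP wording and recoding of data already planned. The headline becomes an odds ratio plus a dose ratio. Because about half of patients are high, the odds ratio exceeds the risk ratio: with simulated percentages of 55.6% and 49.4% (Simulation 1, dose ratio 1.25), the odds ratio is (0.556/0.444)/(0.494/0.506) = 1.28 and the risk ratio 0.556/0.494 = 1.13. The dose ratio is sensitive to very heavy users. On the same assumed inputs and unadjusted, its 95% CI is about ×/÷ 1.28 at 3,000 patients and ×/÷ 1.15 at 10,000; the odds ratio has similar precision (1.28 and 1.14). Patients diagnosed only after BPD diagnosis leave the exposed group in the logistic analysis, which makes that group smaller.
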